- SF-36, to measure overall health-related quality of life; and
- EQ-5D, a preference-based measure of health-related quality of life.

Resource use will be monitored within the pilot study with the view to informing the design of economic measures within the subsequent definitive trial. Unit cost data will be obtained from national databases such as the BNF and PSSRU Unit Costs of Health and Social Care. Where these are not available, the unit costs will be estimated using primary research methods in consultation with the UHCW finance department. The cost consequences following discharge, including NHS costs and patients' out-of-pocket expenses will be recorded via a short questionnaire which will be administered at 3, 6 and 12 months post treatment. Patient self-reported information on service use has been shown to be accurate in terms of the intensity of use of different services.⁵⁹ An assessment will be made of the best possible way of identifying, measuring and valuing the economic costs and health consequences of hip arthroscopy for FAI for application within the subsequent definitive trial.

Follow-up

We will use techniques common in long-term cohort studies to ensure minimum loss to follow-up, such as collection of multiple contact addresses and telephone numbers, mobile telephone numbers and email addresses. Considerable efforts will be made by the trial team to keep in touch with patients throughout the trial by means of newsletters etc.

Follow-up questionnaires will be administered by post or email with 3 reminders and a final telephone call for minimum data collection.

| Time | Data to be collected |
|-----------|---|
| Baseline | NAHS, IHOT-33, SF-36, EQ5D; preoperative imaging |
| 6 weeks | Complication records, operation proforma, operative video, postoperative imaging |
| 3 months | NAHS, IHOT-33, SF-36, EQ5D; complications; conservative care log; economics questionnaire |
| 6 months | NAHS, IHOT-33, SF-36, EQ5D; complications; conservative care log; economics questionnaire |
| 12 months | NAHS, IHOT-33, SF-36, EQ5D; complications; conservative care log; economics questionnaire |

Table 2: Follow up measures

Good Clinical Practice

The trial will be conducted in accordance with the Medical Research Council's Good Clinical Practice (MRC GCP) principles and guidelines, the Declaration of Helsinki, Warwick Clinical Trials Unit SOPs, relevant UK legislation and the Protocol. GCP-trained personnel will conduct the trial.

Consort

The trial will be reported in line with the CONSORT statement.

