
The provisional non-operative care protocol is:

- Anti-inflammatory drugs for 2 to 4 weeks.
- Stretching exercises explained and initially supervised by a Chartered Physiotherapist for 2 to 3 weeks in the form of stretching exercises to improve hip external rotation and abduction in extension and flexion.
- Patients followed up every 2 weeks for 2 months by their physiotherapist

- Further assessment of the normal range of hip internal rotation and flexion after the acute pain has subsided. Physiotherapist determines the safe range of movement to avoid FAI.
- Patients are instructed to adapt to their safe range of movement and perform activities of daily living with minimal friction.
- Modification of activities of daily living predisposing to FAI (e.g. hip internal rotation associated with flexion and adduction. Patients are taught to avoid running on a treadmill or narrow straight trails to prevent internal rotation of the lower limbs. Such activities are to be replaced by running in a zigzag and wide courses (requiring some abduction and external rotation during turns). Cycling is to be avoided if possible, as this involves hip flexion and internal rotation at the same time. When cycling is unavoidable, the patients are advised to externally rotate the legs to give some rest to their hip and also elevate the bicycle seat to avoid deep hip flexion. Patients avoid sitting continuously for a long time with the spine fully straight and the hip in flexion; when sitting, lean back every 5 or 7 minutes (to decrease hip flexion) is encouraged.
- Patients followed up every 2 months for 4 months.
- Patient progresses to further advanced exercises when range of movement is full, walking is normal and pain free and muscle strength is greater than 70% of the uninvolved side in all directions. The goals of this stage are the restoration of muscular and cardiovascular endurance, and the improvement of balance reactions. Return to social sport should be possible at this stage.
- Some but not all patients will require sports specific training. Those who take part in competitive sport will certainly benefit from further strengthening and more sports specific exercise. Training regimes for this stage should be developed in conjunction with sports club physiotherapists or personal trainers.

Quality assurance of treatments

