In a full trial, quality assurance of both interventions will be essential in order to ensure that any true effect is measured. One objective of this feasibility study will be to design and test methods for this quality assurance. This may be particularly challenging for the surgical intervention because it is not clear that surgeons will accept the critical judgments of their peers, particularly when most of the surgeons performing these operations consider themselves to be innovators and experts.

For each operation, we will prepare a vignette comprising: an operative proforma describing the operation which has been performed; clips of intraoperative video; and post-operative 3-D shape imaging with a single sequence MR proton density volume acquisition. We have tested each of these elements and believe that they allow a comprehensive assessment of the quality of the surgery that has been performed. For each participant, this vignette will be analysed by an international expert group comprising [name] (secretary of the British Hip Society, with a usefully skeptical stance on FAI surgery), [name] (USA; chairman of the Research Committee of the International Society for Hip Arthroscopy), [name] (Switzerland; one of the investigators credited with developing the early understanding of FAI), [name] (Australia; a highly respected high-volume arthroscopic hip surgeon), and [name] (UK; an expert in musculoskeletal radiology).

For conservative care, participating physiotherapists will record full details of the advice and treatments, number of treatments, non-attendance, and any adverse events for each patient on specifically designed case report forms. Process records of therapies including physiotherapy, prescribed analgesia, intra-articular injections and advice. These case report forms will be audited against the physiotherapists clinical notes to ensure accuracy and to determine protocol compliance by participating physiotherapists before collation by the research team in order to fully describe the interventions delivered. Where protocol deviations are noted, these will be discussed with the physiotherapists involved in order to enhance compliance with the agreed intervention protocol.

Outcome Measures

The primary outcome measure will be the Non-Arthritic Hip Score

(NAHS) Secondary outcome measures will be:

- IHOT-33, a possible alternate primary outcome instrument for a full trial;

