3.8 Adverse events

3.8.1 Adverse event management

Adverse events (AE) are defined as *any untoward medical occurrence in a clinical trial patient and which do not necessarily have a causal relationship with the treatment*. All AEs will be listed on the appropriate Case Report Form for routine return to the 'FASHIoN' central office.

Serious adverse events (SAE) are defined as any *untoward and unexpected medical occurrence that:*

1. *Results in death,*
2. *Is life-threatening*

3. *Requires hospitalisation or prolongation of existing inpatients' hospitalisation,*
4. *Results in persistent or significant disability or incapacity,*
5. *Is a congenital anomaly or birth defect*
6. *Any other important medical condition which, although not included in the above, may require medical or surgical intervention to prevent one of the outcomes listed.*

All SAEs will be entered onto the reporting form and faxed to dedicated fax at WMSCTU within 24 hours of the investigator becoming aware of them. Once received, causality and expectedness will be confirmed by the CI. SAEs that are deemed to be unexpected and related to the trial will be notified to the Research Ethics Committee (REC) within 15 days. All such events will be reported to the Trial Steering Committee and Data Monitoring Committee at their next meetings. SAEs that may be expected as part of the surgical interventions, and that do not need to be reported to the main REC are: complications of anaesthesia or surgery (wound infection, bleeding or damage to adjacent structures such as nerves, tendons and blood vessels, delayed wound healing, and thromboembolic events, hip fracture, osteonecrosis and traction related neuropathies). SAEs that may be expected as part of the conservative care interventions and that do not need to be reported to the main REC are: transient increase in pain, delayed onset muscle soreness or mild bleeding at injection or acupuncture needle sites. All participants experiencing SAEs will be followed-up as per protocol until the end of the trial.

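### Only conservative care has a described, audited clinician form for adverse events, so minor harms may be detected more often in that arm than after surgery

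*Protocol*

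**What the plan says.** Section 3.8.1 defines an adverse event broadly, whether or not treatment caused it, and sets a rule for both arms: "All AEs will be listed on the appropriate Case Report Form for routine return". Serious events have their own rule: "All SAEs will be entered onto the reporting form", sent within 24 hours of the investigator becoming aware.

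Section 3.5 describes the instruments:

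- **Conservative care (Quality assurance of treatments).** "participating physiotherapists will record full details of the advice and treatments, number of treatments, non-attendance, and any adverse events for each patient". An audit follows: "These case report forms will be audited against the physiotherapists clinical notes to ensure accuracy".
- **Surgery (same subsection).** Each operation gets a vignette made up of an operative proforma, video clips and post-operative imaging. Its purpose is to judge the quality of the surgery, and no AE item is named.
- **Post-operative rehabilitation (Trial treatments).** A chartered physiotherapist supervises it. No AE form or audit is described.
- **Follow-up schedule (Table 2).** The 6-week row is "Complication records, operation proforma, operative video, postoperative imaging". The 3-, 6- and 12-month rows each read "NAHS, IHOT-33, SF-36, EQ5D; complications; conservative care log; economics questionnaire". No row is restricted to one arm, and the time origin of the 6-week row is not given.

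Under Post randomisation withdrawals, patients who take the other treatment are followed wherever possible and their data collected under the same protocol.

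**The concern.** A rule that all AEs be listed fixes what must be reported once known. It does not make detection equal. In one arm a clinician fills in a form that asks for any adverse event, and the form is checked against the notes. In the other, the scheduled item is 'complications', a term the protocol never relates to its AE definition. Where the word appears in sections 3.8.1 and 3.8.2 it refers to anaesthesia, surgery and hip arthroscopy. The expected effects of conservative care, such as muscle soreness and transient pain, are not called complications there.

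Post-operative rehabilitation is also exercise-based, so it can cause the same soreness. That event would go on an audited form in one arm and might not be counted in the other.

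Two things are at stake. The Data Monitoring Committee reviews safety (section 5.1) and would see minor harms gathered by unlike methods. Section 2.2 also says the pilot is to test the processes proposed for the substantive trial, and harm recording is one of them.

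**Working it through.** The plan gives no figure to reproduce. The check is a count of scheduled recording points, followed by an illustration of what the count could mean.

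**Surgical arm.** Table 2 gives 6 weeks, 3, 6 and 12 months: 4 points.

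**Conservative arm.**
- From Table 2: 3 points (3, 6 and 12 months), or 4 if the 6-week row applies to everyone.
- From the provisional non-operative protocol: "Patients followed up every 2 weeks for 2 months by their physiotherapist" gives about 4 contacts, and a further visit every 2 months for 4 months gives about 2, so about 6 in all. The Best conservative care text instead allows up to 8 sessions.
- If the physiotherapist form is completed at every contact, the total runs from 3 + 6 = 9 to 4 + 8 = 12. Completion at every contact is an assumption; the protocol says only that events are recorded for each patient.

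**Illustration.** Suppose each point independently detects a given minor AE with probability p. Over k points, detection is 1 − (1 − p)^k. The values of p are assumed; the documents give none.

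| p | k = 4 (surgical) | k = 9 | k = 12 | Ratio to surgical |
|---|---|---|---|---|
| 0.3 | 1 − 0.7^4 = 0.76 | 1 − 0.7^9 = 0.96 | 1 − 0.7^12 = 0.99 | about 1.3 |
| 0.1 | 1 − 0.9^4 = 0.34 | 1 − 0.9^9 = 0.61 | 1 − 0.9^12 = 0.72 | 1.8 to 2.1 |

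If the form were instead completed once per patient, the conservative arm would have 3 + 1 = 4 or 4 + 1 = 5 points. At p = 0.3 the ratio would be 1.0 or 0.83/0.76 = 1.1. At p = 0.1 it would be 1.0 or 0.41/0.34 = 1.2. So the count alone can give anything from no excess to about two-fold.

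Two features lie outside this calculation. A 'complications' item may pick up minor AEs less well than an AE item, which would raise the ratio. AEs noticed during rehabilitation and listed under section 3.8.1 would lower it.

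**Crossover.** The conservative package lasts at least 12 weeks. If the 6-week row is timed from randomisation, surgery after a completed package falls after that row (12 > 6). If the row is timed from surgery, it does not. In either case the operation still produces the vignette, and events within the 12-month follow-up remain under the later Table 2 rows and the AE and SAE rules.

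**The case against.** The strongest reply is that section 3.8.1 already requires all AEs and SAEs to be reported in both arms. On this view the physiotherapist form is a quality-assurance record that describes the treatment delivered, not a harm schedule. The pilot estimates recruitment rate, section 4.2 plans no between-arm harm comparison, and section 4.1 leaves form design to the trial coordinator. With about 0.30 × 60 = 18 patients randomised, roughly 9 per arm, no AE comparison would be informative.

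Much of this stands, and it limits the stakes. It does not remove the asymmetry. The form does record any adverse events, whatever its purpose, and the protocol describes neither such a form nor such an audit for the rehabilitation physiotherapists.

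Three stronger readings are tempting, and the documents do not support them.

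- **Surgical harms are recorded only once, at 6 weeks.** Table 2 lists complications again at 3, 6 and 12 months.
- **There is a near three-fold detection bias.** Setting 6 physiotherapy contacts against 1 surgical record at p = 0.3 gives 0.88/0.30 = 2.9. That comparison leaves out the later rows and treats every treatment visit as an AE recording, which the text does not say.
- **Harms of crossover operations go unrecorded.** The 6-week row has no stated origin. Its contents suggest timing from surgery, and the economics questionnaire is timed from treatment. Only the 6-week complication record might be missed.

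**Conclusion.** The point holds as a cheap improvement. A dedicated, audited, clinician-completed AE form is described for conservative care alone, and surgical patients have scheduled complications plus the general rules. Minor AEs may therefore be detected more often under conservative care.

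The size is not known. The ratios of about 1.3 (p = 0.3) and 1.8 to 2.1 (p = 0.1) depend on a form at every contact, independent detection, equal sensitivity of both kinds of item, and assumed values of p. They show direction and plausible scale, and they are not estimates. Serious events are little affected, because one investigator-reporting rule covers both arms. The effect on crossover operations depends on a time origin that the protocol does not state. The pilot's recruitment estimate is untouched.

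**What to change.** 1. Give physiotherapists who deliver post-operative rehabilitation the same AE section, using the section 3.8.1 definition, and the same audit against clinical notes as those who deliver conservative care.
2. In Table 2, replace 'complications' with that AE item at common time points in both arms. Base any between-arm harm summary on those points only.
3. Add a footnote to Table 2 saying that the 6-week complication record is timed from, and triggered by, any hip arthroscopy in either arm.

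The cost is a form revision and a footnote, a few minutes of form-filling for the rehabilitation physiotherapists, some audit work, and one record for each crossover operation, in roughly 18 randomised patients. It needs no new visit or assessor and changes neither treatment.

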3.6 Integrated qualitative study of recruitment (IQR)

Purpose

The aim of the IQR is to understand the recruitment process in the early stages, so that any difficulties related to design or conduct can be raised and changes put in place. The IQR will also be used to determine any staff training that needs to be developed. The IQR is intended to provide information about recruitment as it happens, and to provide the basis for the plan of action to improve it. The ethnographic nature of the IQR means that the research moulds itself around the needs of the trial and is completed when theoretical saturation is reached (that is, new data collection does not materially add to the findings).

Patient pathway through eligibility and recruitment

A comprehensive process of logging of potential RCT patients through screening and eligibility phases will be put in place in order to ensure compliance with the CONSORT checklist and to monitor recruitment. The trial team will develop a flow chart of the anticipated recruitment pathway that maps the patient's journey beginning from the point of diagnosis to making a decision about participation in the RCT.

These logs will give an indication of the numbers of eligible patients and particular points where they are 'lost' from the RCT. They will also indicate levels of equipoise – as evidenced by the numbers rejecting participation in the RCT and the selection of particular treatments.

In-depth interviews and investigator meetings

In-depth, semi-structured interviews will be conducted with two groups:

- Members of the TMG, including the CI and those most closely involved in the design, management, leadership and coordination of the trial;
- Clinical staff in each of the participating centres.

Interview topic guides will be used to ensure similar areas are covered in each interview, based on those used in previous studies, but also encouraging the informants to express their own views about the RCT and any recruitment challenges expected or experienced.

Clinicians who recruit to the trial will also be asked questions about their knowledge of the evidence and personal views about equipoise; the recruitment pathway, how they feel the protocol fits their clinical setting and any adjustments they think are needed. They will also be asked how they explain the RCT, the interventions and controls to patients, and the randomisation process.

The IQR team will observe meetings of the TMG and TSC. The IQR researchers will discuss the agenda with the CI, with the aim of fostering discussion, particularly about issues of eligibility and equipoise if these have emerged from the early findings. The meetings will also be a forum to discuss the findings of the IQR, and to deliver training or advice about recruitment.

Interviews and meetings will be audio-recorded and transcribed. Recordings may be transcribed verbatim whole or in selected parts, as necessary for comprehensive or targeted analysis. Transcripts and notes will be analysed thematically by the IQR researcher, using techniques of constant comparison and case-study approaches. This will involve detailed coding, and then comparing emerging themes and codes within transcripts and across the dataset looking for shared or disparate views among TMG members, specialist clinicians and recruiters, and within or between centres or specialties. The coding will be carried out using qualitative data analysis software such as ATLAS-ti or NVivo. The initial coding will be cross-checked by another researcher and discussed with the IQR PI, with inconsistencies resolved by discussion. Detailed descriptive accounts of the themes and cases will then be produced by the IQR researcher.

Interviews and meetings will provide data about: the evidence underlying the RCT, including the importance of the question and the commitment of staff to it, as well as individual clinical equipoise; the application of the protocol in clinical centres and any logistical issues; and suggestions about reasons for recruitment difficulties and potential solutions from those working closely within the RCT.

Audio-recording of consultation and recruitment appointments

Clinicians will scrutinise referral letters before clinics to identify potential FAI patients. In at least one centre (initially Coventry), patients will be contacted in advance of their first consultation to request their permission for their consultation to be recorded.

Those who have a diagnosis of FAI will then be given patient information about their condition, its possible treatments, and about the FASHIoN trial. They will be invited to attend a trial information consultation, which will be recorded.

Audio-recordings of appointments will be analysed as described above for interviews, with the addition of some of the techniques of focused CA – conversation analysis – pioneered in previous studies. CA techniques will be used to identify and document aspects of informed consent and information provision that is unclear, disrupted or hinders recruitment. Recordings will be listened to by the researcher and notes made about the content of the appointment, including the basic content covered,

the order of presentation of RCT arms and other treatment options, time spent on interventions and controls, and time spent describing both the RCT design and the randomisation process. An assessment will be made as to whether the appointment is recruiter- or participant-led, and also the degree to which there is evidence that the participant has understood the key issues of equipoise, randomisation, participation in the RCT, the option to choose their treatment, and the option to withdraw from the research at any time.

RIAS (the Roter Interaction Analysis System) coding will also be applied to the information consultation recordings. This is a well established system for analysing clinical consultation processes. It provides a detailed description of what happens during consultations, including: the nature and content of what is discussed; whether questions are asked in an open or closed manner; the relative contributions of clinicians and patients; the types of verbal utterances made e.g. clinicians showing approval, empathy, making partnership statements; the time spent in different consultation phases; and an affect rating for each consultation. RIAS coding will be imported into SPSS to provide a quantitative analysis of these different consultation mechanisms and characteristics, which will complement the other two analytic approaches.

The IQR researcher will document these details and provide an account for the IQR PI. When at least three recordings have been analysed, the IQR researcher and PI will decide what confidential feedback will be given to the recruiter. Issues to be fed back to the RCT CI/TMG, or to be used anonymously in training programmes will be discussed and defined.

These data will form the basis for feedback to individuals and for development of training programmes.

Study documentation

The CI/TMG will be working on the RCT protocol, ethical approval and governance documents during the early stages of the IQR. PIS and consent forms will be scrutinised by the IQR team to identify aspects that are unclear or potentially open to misinterpretation, the clarity of the lay presentation of the evidence, and the balance of information on the different arms in the RCT and its adverse events. The information from the study documents will be compared with the findings from the interviews and recorded appointments, to identify any disparities or improvements that could be made.

Feedback to CI/TMG

The IQR team will present summaries of anonymised findings emerging from their work to the CI and TMG, identifying any aspects of RCT design and conduct that could be hindering recruitment with the supporting evidence. There are likely to be several meetings regularly during the feasibility phase of the study to present these findings and discuss a plan of action to try to improve recruitment, if this proves necessary. The plan is likely to include some or all of: reconsideration of study information, advice about presenting the study, discussions about equipoise or evidence, issues with patient pathways, and logistical issues in particular centres. These may be addressed by new PIS, documents, changes to the protocol, or training for recruiters in the presentation of RCTs in general or the specific RCT.

Evaluation

Numbers of eligible patients, and the percentages of these that are approached about the RCT, consent to be randomised and immediately accept or reject the allocation will be assessed before the plan of action is implemented, and regularly afterwards to check whether rates are improving.

